9. PARTICIPANTS

Number of Participants

Twenty four male individuals from or living in the region of Luxembourg will be recruited for this study. The number of participants is based on a randomized block design, constituting of 6 blocks of 4 subjects, each will be served different sequences of test meals (A, B, C/A, C, B/B, C, A/B, A, C/C, A, B/C, B, A) in order to cancel out any potential effect of sequence of meals (See scheme of test meal sequences in Figure 2).

Our aim would thus be to recruit 24 subjects, and try our best in terms of follow-up and interaction to keep them in the study. However, should several subjects opt to leave the study, we would still, even with only ca. 15 subjects, reach

sufficient statistical strength to see small differences in absorption in this cross-over study. For example, a difference in fractional absorption between 10% and 8% could be resolved already in a pairwise design with a SD of absorption difference of ca. 2.5% for an alpha of 0.05 and a power of 80% (<http://biomath.info/power/prt.htm>). As each subject will act as his/her own control, this could be seen as a realistic estimate. The reason for recruiting male subjects only is that carotenoid plasma concentrations are likely influenced by the monthly cycle of women [29], and we preferred not to undergo any risk in this regard – this position was also accepted by the FNR (Grant CAROPROT, C16/BM/11320230).

Inclusion criteria

- healthy and free living;
- men;
- age between 20 and 50 years old;
- Body-Mass-Index (BMI) <30 kg/m²
- non-smokers (abstinent for more than 2 years);

Exclusion criteria:

- suffering from any metabolic disease that may cause digestive disturbances (such as Crohn's disease or colitis);
- malabsorption disorders;
- BMI over 30 kg/m²;
- hyperlipidaemia (triglycerides and total cholesterol over 200 mg/dl)
- any individuals following a special diet that is not compatible with wash-out periods or test meals (vegetarian, gluten-free or diabetic);
- regular consumption of more than 5 portions (80-100 g) of fruits and vegetables per day;
- being on medical treatment or consuming any medication for chronic conditions or recent illness (e.g. antibiotics);
- consuming regularly dietary supplements;
- abnormally high or low values of plasma circulating carotenoids;
- tobacco smoking;
- frequent alcohol consumption (over 2 glasses per day);
- food allergies or intolerances that are not compatible with test meals (e.g. gluten or milk intolerance);

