The first washout week starts on day 1 after the preliminary visit and will have a duration of 14 days during which the participants will be asked to stay on a low carotenoid diet (i.e. to avoid the intake of colored fruits and vegetables), to reduce the basal levels of blood circulating carotenoids. This first appointment will be followed by a 1 week washout period, during which he/she will continue on a low carotenoid diet (3rd week of washout diet). At the end of the 3rd week of washout, the second appointment at the CIEC will take place. The procedure for this day is the same as mentioned above. The second appointment is followed by the 4th and last washout week and at the end the participant will have the 3rd and last appointment at CIEC, which will be identical to the other visits. For all washout periods the participants will be asked to fill a provided food journal, on a daily basis, where they will write down what they have eaten during the day. This will be used to check compliance with the washout period and better interpret personal data.

Please find in Figure 3 a scheme of the participant’s schedule during the trial phase.

[figure not shown]

Figure 3 – Representative scheme of the participants’ schedule during the trial phase.

Data management:

The data collected in this study (lifestyle questionnaires, urine and blood samples, carotenoid plasma and plasma-TRL fraction analysis -a special fraction isolated from blood plasma-, biometric measures) will be used to investigate the influence of dietary proteins on the bioavailability, that means uptake and usage of carotenoids by the human body. The results of the investigation will possibly be published in international scientific journals without detriment to the subject's privacy.

The data collected will be treated in a strictly confidential manner and will be kept up to five years after completion of the study. The processing of the data will be done by means of a code (pseudonimisation). This code does not identify participants and will only be used for the scientific treatment of the results.

According to the provisions of the amended Grand-Ducal Law of 2nd August 2002 on the protection of individuals with regard to the processing of personal data, a notification will also be submitted to the 'Commission Nationale pour la Protection des Données' (CNPD).

Insurance:

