11. STATISTICAL ANALYSIS

The baseline corrected AUC for carotenoids will be calculated by the trapezoidal approach, using the PK functions plug-in for Microsoft Excel. Negative values, if occurring, will be included as such.

Mean AUC between the test meals will be compared by a repeated measures ANOVA design (i.e. each subject will be compared against himself at 3 time points), followed by post-hoc test comparisons (Fisher protected LSD test) given a significant Fisher-F test. No log-transformation will be carried out, but AUC values will be baseline corrected. Thus, a model with the observed dependent factor baseline-corrected-AUC for each carotenoid (lycopene, beta-carotene) and the triglycerides will be run, with subject, randomization sequence, test meal as fixed factor and baseline carotenoid concentration as a covariate.

Normal distribution will be verified by Q-Q-plots and Kolmogorov-Smirnoff tests.

Non parametrical analysis (Friedman tests followed by individual t-tests) may be chosen in case data is not normally distributed, though based on earlier studies data normally follows normal distribution. Log-transformation will not be carried out.

P-values below 0.05 will be interpreted as statistically significant (2-tailed). Data analysis will be performed with SPSS 19.0 for Windows (SPSS Inc., Chicago IL).

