2.4 Trial design

This is a post-prandial double blinded, randomized and controlled cross-over study with 3 periods and six sequences.

A 6x3 Williams Crossover design is applied for the six sequences. Equal allocation of six patients per sequence is planned. Patients meeting the inclusion criteria will receive three different interventions (2 different meals with added protein sources and one control meal where no protein is added) at three different time points following a one-week washout period.

A	B	C
B	C	A
C	A	B

C	B	A
A	C	B
B	A	C

Figure 1: 6x3 Williams Crossover Design

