2.6 Sample Size

It is assumed that two different outcomes will be tested as dependent variables and all pairwise comparisons will be performed. First lycopene and then beta-carotene will be tested. This will lead to three statistical tests per carotenoid readout: with the original alpha risk of 0.05 the corrected alpha risk would then be $0.05/6=0.083$ i.e. 0.83%. The Bonferroni adjustment will be used to keep the family-wise error at the specified error level and thus with the total number of pairwise comparisons equal to 6 each pairwise test is at the two-sided 0.83% significance level.

Area under the time – carotenoid concentration is assumed as main outcome for the sample size calculation.

When there are 2 outcomes (lycopene and beta-carotene), 3 treatments and a sample size of 4 in each of the 6 sequences, a 6x3 Williams Crossover inequality test of paired differences will have 96% power to detect a minimum difference of 4% of the area under time curve (AUC) (difference between 20% and 24% of AUC) or greater, assuming that the standard deviation of the paired differences is 4% at the 0.83% significance level. This leads to a total sample size of N=24 participants.

In case of one drop-out per sequence (n=3 per sequence), the power will reduce to 83%, which will still provide sufficient statistical strength. Sample size calculation was performed in nQuery 8 (version 8.3.1.0).

[figure not shown]

Figure 3 Power (%) vs. Sample Size per Sequence; minimum difference = 4%, SD = 4%, significance level = 0.8%

Figure 4 Power (%) vs. Minimum Expected Difference; n per sequence = 4, $SD = 4\%$, significance level = 0.8%

[figure not shown]

Figure 5 Power (%) vs. Standard deviation; $n=4$ per sequence, mean difference = 4%, significance level = 0.8%

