4.3 Withdrawal/ follow-up

Participants are free to withdraw from the study at any moment if they desire to do so. However, we will try our best in terms of follow-up to keep subjects in the study. Any participant showing new medical problems that are not easily explained (e.g. colds) or that requires the use of medication (e.g. antibiotics) will be withdrawn from the study.

Subjects that have at least completed 2 clinical days will be kept for statistical analysis, and given that subjects agree to keeping their data. Otherwise, the cases will be removed from analysis.

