5.2 Analysis methods

The primary endpoint, AUC of either lycopene or beta carotene will be analysed using a linear mixed model using randomization sequence and treatment (test meal) as fixed terms and patient within sequence as a random term taking into account the cross-over design as described in chapter 5 of "Cross-Over Trials", Senn (2002). Baseline will be included as a co-variate.

Assumptions of normality and equality of variance will be verified by normality plots and boxplots, respectively. If data is non- normally distributed, log transformation will be attempted.

Non-parametrical analysis (Friedman tests followed by Wilcoxon- Mann- Whitney test) may be chosen in case data is not normally distributed, if log-transformation is not successful, though based on earlier studies data normally follows normal distribution.

The secondary endpoints - triglycerides, and if feasible additional carotenoids (see 5.1 above) will be analysed by the same methodology.

A linear mixed model will be first performed for each main outcome, with either baseline corrected AUC of lycopene or beta-carotene as the observed, dependent variable, and randomization sequence, test-meal as the independent variable (fixed factor) and patient within sequence as random factor. Pairwise comparisons of the intervention will be performed by means of Tukey's post-hoc test. Additionally, sensitivity analysis with the original outcomes (lycopene or beta-carotene) as dependent, randomization sequence, test meal and baseline concentration of the outcome as fixed factors and patient within sequence as random factor. 95% confidence intervals will be reported for the main outcomes.

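### The three-period cross-over model has no period term, and SAP 5.2 gives two different primary models on the baseline covariate

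*SAP*

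**What the plan says.** **Design.** SAP 2.4 describes a "randomized and controlled cross-over study with 3 periods and six sequences". Protocol section 9 says the six meal orders are used "in order to cancel out any potential effect of sequence of meals". Under Protocol section 10 (Participants' Schedule), the visits follow 2, 3 and 4 weeks of a continuing low-carotenoid diet that is meant "to reduce the basal levels of blood circulating carotenoids".

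**Model terms.** The first paragraph of SAP 5.2 lists "randomization sequence and treatment (test meal) as fixed terms and patient within sequence as a random term", refers to a textbook chapter on cross-over trials, and adds baseline as a covariate. The last paragraph restates the model for baseline-corrected AUC with "randomization sequence, test-meal as the independent variable (fixed factor) and patient within sequence as random factor"; baseline is not in that list. The sensitivity model in the same paragraph uses the original outcomes and adds baseline concentration. Protocol section 11 has a model "with subject, randomization sequence, test meal as fixed factor and baseline carotenoid concentration as a covariate". None of these lists contains period or visit.

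**Baseline elsewhere.** SAP 2.2(e) and 5.1 put the 0h concentration in the model as a covariate. SAP 2.2(c) mentions it as a covariate only for the sensitivity analysis of unsubtracted data.

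**Incomplete subjects.** SAP 4.3 says "Subjects that have at least completed 2 clinical days will be kept for statistical analysis"; SAP 3.2 allows any two of the three visits.

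**The concern.** **Period.** Balancing the meal orders keeps a visit effect from biasing the meal contrasts when every subject completes. It does not take that effect out of the error; only a period term does. Diet exposure lengthens from visit to visit, so a visit effect is plausible, although the documents do not report one in the AUC. At stake are precision and, because two-visit subjects are kept, protection against bias if lost visits fall unevenly across meals.

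**Baseline.** Two primary models are on paper, and the choice between them could be made after the data are seen. Under one of them the planned sensitivity analysis tests nothing.

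**Working it through.** **Inputs.** SAP 2.6 gives 24 subjects (4 per sequence), a target difference of 4 points, a two-sided alpha of 0.05/6 = 0.00833, and power "assuming that the standard deviation of the paired differences is 4" points. If that SD is pure error, the within-subject variance is 4²/2 = 8 (SD 2.83). Assumed, because the documents give no figure: linear drift of d points per visit, d = 0 to 3.

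**1. The plan's own figure.** Noncentral t with ncp = (4/4)√N and N − 6 degrees of freedom: N = 24 (ncp 4.90, 18 df) gives 96.2%; N = 18 (ncp 4.24, 12 df) gives 83.5%. The SAP states 96% and 83%, so both reproduce. Paired differences pooled within sequence carry no period drift in their error, so the stated power appears to rest on an error free of drift.

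**2. Period omitted, complete data, no 0h covariate.** A subject's visits sit at −d, 0 and +d, which adds 2d² per subject, or 48d² over 24 subjects. Meals are balanced over visits, so all of this falls into the residual, which has 72 − 24 − 2 = 46 df:

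error variance = (46 × 8 + 48d²)/46; SE of a meal contrast = √(2 × variance/24).

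| d | Error variance | SE without period | Power without period |
|---|---|---|---|
| 0 | 8.00 | 0.82 | 98.1% |
| 1 | 416/46 = 9.04 | 0.87 | 97.1% |
| 2 | 560/46 = 12.17 | 1.01 | 92.4% |
| 3 | 800/46 = 17.39 | 1.20 | 78.7% |

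With period in the model (44 df), the SE is 0.82 and power about 98% at every d. At N = 18 and d = 2, power is 77.1% without period and 91.4% with it.

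**3. Period omitted, 0h covariate included.** These are simulated fits, with within-subject noise in the 0h level assumed equal to its fall per visit. With drift unrelated to the 0h level and N = 24, power without and with period is:
- d = 1: 97% and 98%
- d = 2: 94% and 97% (SE 0.92 and 0.82)
- d = 3: 88% and 98% (SE 1.03 and 0.82)

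True power with period does not depend on d; the 97/98 difference is simulation error. Halving or doubling the 0h noise moves the 94% to about 97% or 93%. If half of a 2-point drift runs through the 0h level, the loss is under 1 point; if all of it does, there is none. At N = 18 and d = 2, power is 84% without period and 91% with it.

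**4. Type I error, complete data, d = 2, period omitted.** About 0.5% per test with the covariate and 0.1–0.2% without, against a nominal 0.83%. The tests are conservative.

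**5. Lost third visits, period omitted, no covariate.** In a within-subject fit, a two-visit subject who misses the control meal says nothing about protein versus control. Each of the other 24 − m subjects contributes 2/3 to the sum of squares for that contrast. Losing m control-meal third visits leaves drift of m × d uncancelled, so

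shift = m × d/[(24 − m) × 2/3].

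For m = 4 of the 8 such visits and d = 2, this is 8/13.33 = 0.60 points. With the covariate it averages 0.30; with period it is 0. Six third visits lost at random give mean bias 0 with SD 0.26.

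**6. The other reading of the SD.** For any two meals, the squared visit separation averages (1+4+1+1+4+1)/6 = 2. If the SD of 4 already contains the drift, then 16 = 2σ² + 2d², so σ² = 8 − d². No power is then lost against plan (97.8% at d = 2), but adding period would cut the SE from 0.82 to √(2 × 7/24) = 0.76 at d = 1, or √(2 × 4/24) = 0.58 at d = 2.

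**7. Price of the term if there is no drift.** Power goes from 98.09% to 98.05% at N = 24, and from 91.7% to 91.5% at N = 18.

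**8. The duplicate sensitivity analysis.** Over 0–10 h, subtracted AUC = AUC − 10 × C0, where C0 is that visit's 0h value. If subtracted AUC = (sequence, meal, subject terms) + γC0 + error, then AUC = (the same terms) + (γ + 10)C0 + the same error. Meal estimates, SEs and p-values are identical. A numerical check gave the same estimate, SE and p-value from both fits, with C0 slopes differing by exactly 10. If the covariate is left out of the primary model, or the outcome is log-transformed, the two analyses differ.

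**The case against.** - **The textbook chapter may supply a period term.** SAP 5.2 cites it as part of the method, so what can be shown is that period is not named, not that it will be left out. This stands as a limit. However, the SAP spells out its terms repeatedly without period, and an analyst would program that list.
- **No drift in the endpoint is documented.** The diet lowers circulating levels, while the endpoint is the baseline-subtracted AUC in the TRL fraction, after a 14-day washout. The 0h covariate may absorb part or all of any drift. This stands. A drift of 2 points per visit is half the target difference, and at 1 point the loss is about 1 percentage point of power.
- **The uneven-loss case is selective.** Random losses average to zero bias, and 0.30–0.60 is below the planned SE of 0.82. This is fair; the case shows what the period term protects against, not what to expect.
- **Most statements on baseline agree.** SAP 2.2(e), 5.1, the first paragraph of 5.2 and Protocol 11 include the covariate. But the dissenting sentence describes the model to be run first for each main outcome, and SAP 2.2(c) lends it some support.
- **Original outcomes might not mean unsubtracted AUC.** The SAP does not say so outright, but it is the likely reading, and the duplication claim rests on it.

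**Conclusion.** Both points hold and should be fixed; neither invalidates the trial. No written model contains period. With complete data the consequence is lost precision, not bias or excess false positives. The size depends on an unknown drift: negligible up to about 1 point per visit or if the 0h level carries the drift, about 3 percentage points of power at 2 points per visit with the covariate, and about 6 without it. These figures assume linear drift and an SD of 4 that is error only. Uneven loss of visits could also shift the contrasts. In an extreme case (six third visits lost, all for one protein meal, d = 2, no covariate) the estimate falls from 4.0 to 3.0 and per-test type I error rises to 1.7%; with period they stay at 4.0 and 0.8%.

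The baseline contradiction needs no assumption about drift. The duplication of the sensitivity analysis is exact on the untransformed scale when the covariate is in the primary model.

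**What to change.** - State one primary model, in the same words, in SAP 5.2 and Protocol 11: baseline-subtracted AUC on sequence, period (visit 1/2/3, categorical), test meal and that visit's 0h concentration, with subject within sequence random.
- Add period to the secondary and sensitivity models.
- Remove the statement of the primary model in the last paragraph of SAP 5.2 that leaves out baseline, and align SAP 2.2(c).
- Use a sensitivity analysis that can give a different answer, for example the subtracted AUC without the 0h covariate.
- Optional: in Protocol 11, make subject random or drop sequence, which is redundant beside a fixed subject term. The meal contrasts do not change.

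The cost is wording in two documents and 2 residual degrees of freedom. No new data are needed and the sample size does not change.

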3.2 Adherence and protocol deviations

The adherence to the intervention will be assessed based on the combined entry in the participant's study log-book, which each participant will fill out. Deviations will be discussed between the PI, CIEC and statistician and decisions for removal of subjects and collected data from the study be discussed on a case-by-case scenario. Deviations will be :

- a) Not fasting at least 10 h overnight
- b) Eating something in the morning before any of the test-meals served at the LIH.
- c) Not consuming the entire test meal within a maximum of 30 minutes.
- d) Not conducting any washout before the study.
- e) Dropping out after the first clinical day

When subjects have completed successfully at least 2 clinical visits (any 2 out of 3), their data will be analysed, if the permission from the subject is granted.

Minor deviations from the protocol that will therefore be tolerated (not dropping out):

- Drinking water during the overnight fasting
- Eating carotenoid containing foods during the washout-period, as long as the individual food items in question are listed in the volunteer's booklet
- Up to 2 missing time-points (any 2 out of 8) during the clinical days.

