3.3 Analysis population

The population is healthy adult males, living in Luxembourg, and the intervention will follow the intention to treat standard. The ITT population is all patients randomized to a diet or control arm whatever the arm they were finally allocated. The Per Protocol population is all patients randomized and allocated to an arm that followed strictly the protocol. Participants with major deviations to the protocol will be excluded from the PP population.

4. Trial Population

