5.3 Missing data

Individual time-points, if missing, during the clinical days will be estimated by using multiple imputations (Multivariate Imputation by Chained Equations).

For complete missing data-sets (1 or 2 clinical days missing), see withdrawal/follow-up.

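### The overall test in the SAP's optional rank fallback (Friedman) needs all three meals, so it loses the two-visit participants whom SAP 3.2 and 4.3 keep for analysis

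*SAP*

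**What the plan says.** **Who is kept.** SAP 3.2: "When subjects have completed successfully at least 2 clinical visits (any 2 out of 3), their data will be analysed". SAP 4.3 repeats it: "Subjects that have at least completed 2 clinical days will be kept for statistical analysis". Both depend on the participant's permission. SAP 3.3 sets a wider frame: "The ITT population is all patients randomized to a diet or control arm whatever the arm they were finally allocated".

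**What is imputed.** SAP 5.3: "Individual time-points, if missing, during the clinical days will be estimated by using multiple imputations". For a whole visit it only points elsewhere: "For complete missing data-sets (1 or 2 clinical days missing), see withdrawal/follow-up". The section it points to (4.3) holds the retention rule and no imputation.

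**How the data are analysed.** The design is a "randomized and controlled cross-over study with 3 periods and six sequences" (SAP 2.4). The primary analysis in SAP 5.2 is a linear mixed model with "patient within sequence as a random term taking into account the cross-over design". If normality fails and a log transformation does not help, SAP 5.2 offers a rank route: "Non-parametrical analysis (Friedman tests followed by Wilcoxon- Mann- Whitney test) may be chosen in case data is not normally distributed". No rank test for incomplete data is named, and nothing says how a two-visit participant enters this route.

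**The concern.** A mixed model can use a participant with two of three AUCs. The Friedman test cannot, because its score is the ranking of all three meals within one person. If the fallback is used, the overall rank test of a primary endpoint therefore runs on fewer people than the retention rule promises, and the analysis set changes with the test. Someone would have to decide how to handle those participants after the data are in hand.

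The fallback is optional but not remote. The endpoint is a baseline-subtracted AUC from which negative area is deducted (SAP 2.2 and 5.1). Zero or negative values are thus possible, and a plain log transformation is then undefined. Missing visits are also foreseen, since SAP 3.2, 4.3 and 5.3 each make a rule for them.

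**Working it through.** **1. The plan's own figure.** SAP 2.6 gives a difference of 4, an SD of paired differences of 4 and a two-sided level of 0.83%. It states power of 96% with 24 participants and 83% with 18. Use a noncentral t with noncentrality (4/4)·√N and N − 6 degrees of freedom:
- N = 24: noncentrality 4.90, df 18, power 96.2%.
- N = 18: noncentrality 4.24, df 12, power 83.5%.

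Both figures reproduce, so the sample size is not in question. SAP 2.6 also fixes the reference effect at 4/4 = 1.0 SD of paired differences.

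**2. Why Friedman needs three values.** With k = 3 meals, n participants and rank sums R_j, the statistic is

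Q = 12/[n·k·(k+1)]·ΣR_j² − 3n(k+1) = ΣR_j²/n − 12n.

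It presumes that every participant contributes the ranks 1, 2 and 3. A standard routine given 24 × 3 = 72 values with one missing returned no statistic. It ran only after that participant was removed.

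**3. A rank test that accepts two values.** Skillings-Mack gives a participant with k_i meals the scores √(12/(k_i+1))·(rank − (k_i+1)/2).
- Three meals: √3·(rank − 2), that is −1.73, 0 and +1.73.
- Two meals: 2·(rank − 1.5), that is −1 and +1.

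The meal sums are combined in a quadratic form referred to chi-square with 2 df. With complete data it becomes Σ(R_j − 2n)²/n. Since ΣR_j = 6n, this is ΣR_j²/n − 24n + 12n = ΣR_j²/n − 12n, the Friedman statistic.

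**4. What is discarded.** The documents give no number of two-visit participants. Assume six of 24, with the missing meal spread evenly (two per meal).
- Kept under SAP 3.2 and 4.3: 24 participants, 72 − 6 = 66 AUCs.
- Used by Friedman: 18 participants, 18 × 3 = 54 AUCs.
- Lost: 6/24 = 25% of participants and 12/66 = 18% of the observed AUCs.

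With one such participant the loss is 1/24 = 4%.

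**5. Power of the overall test.** Simulation: 24 participants, one protein meal shifted, independent within-person errors scaled to the stated SD of paired differences, and level 0.025 (the per-outcome level in SAP 3.1). The 0.8 SD effect is an added case (0.8 × 4 = 3.2 on the SAP's scale). Runs of 2,000 to 3,000 simulations per setting gave, with six two-visit participants:

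| Errors | Effect (SD of paired differences) | Friedman, 18 complete | Skillings-Mack, all 24 |
|---|---|---|---|
| t, 3 df | 1.0 | about 98% | about 99% |
| t, 3 df | 0.8 | about 92-93% | about 96-97% |
| Normal (reference only) | 1.0 | about 90% | about 95% |
| Normal (reference only) | 0.8 | about 71% | about 80-81% |

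With three two-visit participants the gap is about 0 to 3 points over these settings. Null rejection stayed near 2.5% for both tests. At 3,000 runs the simulation error on a power of 90% is √(0.9 × 0.1/3000) = 0.5 points.

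**The case against.** The strongest reply is that the planned analysis already honours the retention rule. The mixed model is run first and uses two-visit participants, and neither SAP 3.2 nor 4.3 says that every contingency test must use everyone. That stands. A reader might infer that the SAP discards promised data from its primary analysis; it does not.

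Three further inferences also go too far:
- **That these participants vanish from the whole rank route.** They are lost at the overall test. A participant can still enter the pairwise comparison of the two meals he ate.
- **That lost overall power blocks the pairwise tests.** SAP 5.2 only puts the pairwise test after Friedman and states no requirement of significance. The explicit gate is in Protocol section 11 and belongs to the ANOVA with Fisher's LSD. SAP 2.6 and 2.7 are built on pairwise comparisons.
- **That 90% against 95%, or 71% against 80-81%, is the expected loss.** Those figures assume normal errors, under which the fallback would not be triggered. The heavy-tailed rows are the relevant ones.

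The number six is also only an assumption. The drop-out case in SAP 2.6 reduces each sequence to three and counts the lost participants as contributing nothing. It does not describe six people with two visits each. The SAP accepts its 83% power in that case, although that figure is for a pairwise test at 0.83% and is not comparable with an overall test at 0.025.

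What the reply does not remove is the gap in the text: the SAP keeps these participants, imputes nothing for them, and names an overall test that cannot include them.

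**Conclusion.** The point holds, narrowly. SAP 3.2 and 4.3 do not fit the Friedman step of SAP 5.2, and SAP 5.3 does not close the gap. Two conditions must both be met before anything is lost: the optional fallback is used, and at least one participant has exactly two visits.

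Even then the cost is modest. Under the assumptions above, with six two-visit participants and heavy-tailed errors, it is about one point of overall-test power at the SAP's own effect size and about four points at 0.8 SD. The primary mixed model and the sample size are unaffected. The main gain from acting is that the analysis set for the rank test is settled before the data are seen. This is a cheap improvement.

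**What to change.** In SAP 5.2, replace the Friedman test in the fallback by the Skillings-Mack test, and state that the rank analysis uses the same participants as the mixed model under SAP 3.2 and 4.3. If nobody misses a visit, the result is identical to Friedman.

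The cost is one sentence. The downside is that the test would be run in R, which SAP 5.5 lists for validation only, while the main analysis is in SPSS; SAP 5.5 should then name R for this step.

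A weaker alternative is to state that the overall rank test uses only participants with all three visits and to report how many are left out. That removes the ambiguity but not the loss.

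Neither change addresses the Wilcoxon-Mann-Whitney test in the same sentence, which is an unpaired test and a separate matter.
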